### **Arm 1**

**Aim 1:** To test the hypothesis that treatment with BioBoosti has sustained efficacy in treating insomnia.

Our primary endpoint would be insomnia symptoms after 1 year of BioBoosti use as compared to initial symptoms (prior to starting treatment).

Measurement of insomnia will be done in serial comparisons every 3 months for ISI, TST (Total Sleep Time), WASO (Wake After Sleep Onset), as well as PSQI at year 1. We will use repeated measures ANOVA to compare ISI, TST, WASO, at months 3, 6, 9, and 12 and a T-test to compare PSQI at baseline to that after 1 year.

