We do not anticipate all 20 subjects to participate however, interested enrolled subjects will also be offered to continue the treatment for one year for the evaluation of sustained efficacy of BioBoosti as Insomnia Treatment. We *anticipate* enrolling up to 20 subjects at BWH and Faulkner Hospitals.

The study will also look at the effects of the BioBoosti device on sleep and recurrence of headache for patients who have been diagnosed with both insomnia and migraine. The study protocol remains the same besides the treatment with BioBoosti will be for 4 weeks to allow adequate headache assessment.

We anticipate enrolling 20 additional subjects with insomnia and comorbid migraine at Brigham and Women's and Faulkner Hospitals.

Briefly describe study procedures. Include any local site restrictions, for example, "Subjects enrolled at Partners will not participate in the pharmacokinetic portion of the study." Describe study endpoints.

The BWH and FH sleep clinics will be screened for follow-up patients with insomnia. Study staff will notify the treating physician to inform them of a potential subject. The treating physician will first introduce the study to the potential subject. If the subject gives permission and would like to obtain more information regarding the study, study staff will approach them and provide them with a copy of the consent form to review. Study staff may also contact the subject by phone to explain the study and recruit if it is more convenient for the subject. Study staff and a physician investigator will be available to answer all questions. If the potential subject is interested in participating in the study, the Principal Investigator will consult with the treating physician prior to enrolling the subject. If the subject decides to enroll in the study when approached in the clinic, we will proceed with Visit 1 (Enrollment Visit) that same day. The physician investigator will be available to speak with subjects during the consent process.

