#### **Visit 2**

Subjects will be scheduled for a follow up at FH.

Subjective sleep symptoms will be evaluated using validated instruments, including Pittsburgh Sleep Quality Inventory (PSQI), and severity of insomnia - Insomnia Severity Index (ISI), and daytime sleepiness Epworth Sleepiness Scale (ESS), and daily visual analog scale (Karolinska sleepiness scale, KSS).

Objective sleep assessment will be performed using ambulatory 72 hour EEG, using sleep montage per standard AASM criteria, and scored by a registered polysomnography technologist using AASM guidelines. If the subject expresses hesitation because of the 72 hour EEG, then a 48 hour EEG will be offered.

Assessment of sympathetic autonomic nervous system function will be done by measuring cortisol and catecholamine levels using standard assays.

Subjects will continue to wear the actiwatch and complete sleep logs daily.

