### **Visit at 3rd, 6th, 9th months**

- Subjects will complete the Insomnia Severity Index (ISI) and Pittsburgh Sleep Quality Inventory (PSQI).
- They will return the completed sleep logs.
- They will be asked to continue filling out new sleep logs for the following visit.
- They will return the Actiwatch.

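### For ISI, TST and WASO the one-year repeated measures ANOVA omits baseline, so it does not test the stated primary contrast, and a non-significant result over months 3 to 12 would not show that benefit was maintained

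*Combined protocol and SAP*

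**What the plan says.** Specific Aims, Arm 1, Aim 1 gives the purpose of the long-term phase: "To test the hypothesis that treatment with BioBoosti has sustained efficacy in treating insomnia". It then names the contrast of interest: "Our primary endpoint would be insomnia symptoms after 1 year of BioBoosti use as compared to initial symptoms (prior to starting treatment"). Two analyses follow. For insomnia severity and the two sleep measures: "We will use repeated measures ANOVA to compare ISI, TST, WASO, at months 3, 6, 9, and 12". For PSQI: "a T-test to compare PSQI at baseline to that after 1 year".

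On numbers, Research Design and Methods says: "We do not anticipate all 20 subjects to participate however, interested enrolled subjects will also be offered to continue the treatment for one year". The ceiling is given as "enrolling up to 20 subjects at BWH and Faulkner Hospitals".

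On data, the insomnia schedule collects ISI and PSQI before treatment at Visit 2: "Subjective sleep symptoms will be evaluated using validated instruments, including Pittsburgh Sleep Quality Inventory (PSQI), and severity of insomnia - Insomnia Severity Index (ISI"). The actiwatch and sleep logs start at Visit 1. In the Sustained Efficacy Phase, ISI and PSQI are repeated at months 3, 6, 9 and 12, and the actiwatch is worn in the month before each follow-up.

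The documents do not define sustained efficacy numerically. They give no alpha, power, SD, between-visit correlation, loss margin or confidence interval for this aim.

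**The concern.** The primary contrast is 1 year against pre-treatment, but the only test named for ISI, TST and WASO has four levels, none of them pre-treatment. Taken literally, that test asks whether the on-treatment visits differ from one another. A significant F would mean that the outcome moved during the year, through waning or further gain. A non-significant F fits a benefit that lasted, a benefit that faded too little to be seen in a small sample, or no benefit at all.

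At stake is the conclusion of the one-year phase for the insomnia severity score and both sleep measures. If an absence of difference were reported as maintenance, fewer completers and noisier data would make the favourable reading easier to reach.

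**Working it through.** The plan gives no figure to reproduce, so the check has two parts: which contrast each test covers, and what the four-visit F can detect.

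**1. Contrasts covered**

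| Measure | Named test | 1 year vs baseline? | Waning, month 3 to 12? |
|---|---|---|---|
| ISI, TST, WASO | ANOVA over months 3, 6, 9, 12 | No, as written | Omnibus test only, no estimate |
| PSQI | t-test, baseline vs 1 year | Yes | No |

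**2. Chance that the F misses a real loss**

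From the documents: four visits and n of at most 20, with fewer expected. Assumed: n = 10 or 19 analysed, alpha 0.05, equal SD (set to 1) at each visit, compound symmetry with correlation rho from 0.5 to 0.8, and a true 0.5-SD loss by month 12.

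The F has 3 and 3(n−1) df and noncentrality lambda = n × S / (1 − rho), where S is the sum of squared deviations of the four visit means from their average.

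- Linear loss (0, 0.167, 0.333, 0.5): S = 2 × 0.25² + 2 × 0.083² = 0.139
- Loss at month 12 only (0, 0, 0, 0.5): S = 3 × 0.125² + 0.375² = 0.1875
- Step loss from month 9 (0, 0, 0.5, 0.5): S = 4 × 0.25² = 0.25

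Worked case, linear loss, n=10, rho 0.5: lambda = 10 × 0.139 / 0.5 = 2.78. The critical F on 3 and 27 df is 2.96, and the probability of falling below it is 77%.

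Probability of a non-significant F at rho 0.5 / 0.7 / 0.8:

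| Shape | n=10 | n=19 |
|---|---|---|
| Linear | 77 / 64 / 48% | 57 / 33 / 15% |
| Month 12 only | 70 / 53 / 34% | 44 / 19 / 6% |
| Step from month 9 | 61 / 40 / 20% | 30 / 9 / 1% |

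Simulation of the linear case agreed to within about 1 percentage point. With AR(1) correlation (adjacent-visit 0.5 to 0.8) the linear loss was missed 65% to 39% of the time even at n=20. With no change at all over months 3 to 12, the F is non-significant about 95% of the time, simply because alpha is 0.05.

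**3. What the PSQI test adds**

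This is a paired t-test with SD of the difference = sqrt(2(1 − rho)). For a benefit of 1.0 SD at 1 year its power runs from 80% (n=10, rho 0.5) to over 99% (n=19, rho 0.7). If a 1.0-SD early gain has halved to 0.5 SD, it is still significant 29% to 76% of the time over the same range. A significant PSQI result therefore supports benefit at 1 year but does not show that the early gain was kept.

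**4. Would a month-12-minus-month-3 margin test alone be enough?**

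No. A device with no effect has a true loss of 0. With a 0.5-SD margin and n=19, its confidence limit would exclude the margin 54% of the time at rho 0.5 and 90% at rho 0.8. Such a test can carry a claim only after benefit against baseline is shown.

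**5. Precision available**

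The 95% CI half-width for month 12 minus month 3 is t(0.975, n−1) × sqrt(2(1 − rho)) / sqrt(n).

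- n=19: 2.101 × 1.000 / 4.359 = 0.48 SD at rho 0.5; 2.101 × 0.632 / 4.359 = 0.30 SD at rho 0.8
- n=10: 2.262 × 1.000 / 3.162 = 0.72 SD at rho 0.5; 2.262 × 0.632 / 3.162 = 0.45 SD at rho 0.8

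**The case against.** The strongest reply is that the aim does not rest on the ANOVA alone. The same section makes 1 year against pre-treatment the primary endpoint and plans a baseline comparison for PSQI, and both look for a difference. This stands. A reader might infer that sustained efficacy can be claimed only from a non-significant F, or that an ineffective device would be declared effective 95% of the time. The documents support neither. The plan never says that p > 0.05 means sustained, and an ineffective device would also be expected to show no PSQI change from baseline, apart from the drift that any single-group study carries.

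Second, baseline may be implicit in the ANOVA sentence, since it is collected and the stated contrast needs it. That reading is plausible, but the text lists four visits and baseline is not one of them. Nor would the omnibus F settle the matter with baseline added. At n=10 and rho 0.5 to 0.7, a five-level F is significant 87% to 98% of the time if a 1-SD gain is kept, and 73% to 93% if it falls linearly to half. Named contrasts are still needed.

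Third, the miss rates depend on the shape of loss. This also stands. Linear loss is close to the hardest shape to detect: the smallest possible S for a 0.5-SD range over four visits is 0.125, against 0.139 for linear. Near n=19 with high correlation, the F would catch most step losses.

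Fourth, this is a pilot with a voluntary extension, and a formal margin may be out of reach. At 80% power, one-sided 0.025 and no true loss, a 0.5-SD margin needs 34 subjects at rho 0.5 and 21 at rho 0.7. That is a fair reason to make the margin optional. It is not a reason to leave out the baseline contrast or the intervals.

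**Conclusion.** The concern holds for ISI, TST and WASO. The named test does not include the baseline level that the primary endpoint requires. Non-significance among months 3 to 12, in at most 20 subjects, can neither establish maintenance nor separate lasting benefit from none. The PSQI t-test partly covers the aim, for one questionnaire and without addressing waning.

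This conclusion follows from the wording and needs no assumed numbers. The size does depend on assumptions. For a 0.5-SD loss at correlation 0.5 to 0.8, the miss rate is high at n=10 for every shape tried (77% to 20%), and at n=19 it runs from 57% down to 1%. A reader might infer that such a loss would usually go unseen. That is fair for about 10 subjects at moderate correlation, but not for 19 subjects with high correlation and a step loss. The 0.5 SD, the correlations, the shapes and the numbers analysed are all illustrative.

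**What to change.** In Specific Aims, Arm 1, Aim 1:

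1. Include baseline as a level of the repeated-measures model for ISI, TST and WASO. Take baseline TST and WASO from the same source as the follow-up values; the actiwatch is worn before treatment and before each follow-up, whereas no EEG is scheduled in the one-year phase.
2. Make month 12 minus baseline, with a 95% CI, the test of benefit at 1 year for each measure.
3. Report month 12 minus month 3, with a 95% CI, as the estimate of waning.
4. State that a non-significant difference among months 3 to 12 will not be taken as evidence of maintenance.
5. Describe maintenance descriptively, unless an absolute loss margin is fixed before the data are seen. The margin should not be a fraction of the observed month-3 gain, which comes from the same data. If a margin is set, claim maintenance only when the unfavourable confidence limit excludes it and benefit against baseline is also shown.

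The cost is a few sentences of analysis wording, with no new subjects, visits or measurements. The downside is that the trial may be unable to claim maintenance: the expected half-width for month 12 minus month 3 is about 0.3 to 0.5 SD at n=19 and 0.45 to 0.7 SD at n=10. Without a control group, the baseline contrast still shows change from baseline and not device effect.

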### **Visit 4**

Subjects will return after the two weeks of treatment. They will return the completed sleep logs.

Subjective sleep symptoms will be evaluated using validated instruments including, Pittsburgh Sleep Quality Inventory (PSQI), and severity of insomnia - Insomnia Severity Index (ISI), and daytime sleepiness Epworth Sleepiness Scale (ESS), and daily visual analog scale (Karolinska sleepiness scale, KSS).

Objective sleep assessment will be performed using ambulatory 72 hour EEG, using sleep montage per standard AASM criteria, and scored by a registered polysomnography technologist using AASM guidelines. If the subject expresses hesitation because of the 72 hour EEG, then a 48 hour EEG will be offered.

Assessment of urine cortisol and catecholamines will be done as a measure of sympathetic function.

Subjects will continue to wear the actiwatch and complete sleep logs daily.

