## **Visit at 12th month**

Subjects will be asked to return the sleep logs and actiwatch and will be asked to complete the Pittsburgh Sleep Quality Inventory (PSQI), and Insomnia Severity Index (ISI), and daytime sleepiness Epworth Sleepiness Scale (ESS).

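### The one-year PSQI T-test rests on subjects with a month-12 value and leaves three scheduled visits unused, and the companion ANOVA lists no baseline

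*Combined protocol and SAP*

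**What the plan says.** All references are to the combined protocol and SAP.

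- **Endpoint** (Specific Aims, Arm 1): "Our primary endpoint would be insomnia symptoms after 1 year of BioBoosti use as compared to initial symptoms".
- **PSQI analysis** (same section): the only test given is "a T-test to compare PSQI at baseline to that after 1 year". The measurement sentence just before it lists PSQI separately from the quarterly measures, "as well as PSQI at year 1".
- **Other measures** (same section): "We will use repeated measures ANOVA to compare ISI, TST, WASO, at months 3, 6, 9, and 12".
- **PSQI collection**: at baseline, in Visit 2 of the insomnia schedule, before the device is handed out at Visit 3 ("Subjective sleep symptoms will be evaluated using validated instruments, including Pittsburgh Sleep Quality Inventory (PSQI"); after two weeks of treatment, at Visit 4 ("Subjective sleep symptoms will be evaluated using validated instruments including, Pittsburgh Sleep Quality Inventory (PSQI"); at months 3, 6 and 9 ("Subjects will complete the Insomnia Severity Index (ISI) and Pittsburgh Sleep Quality Inventory (PSQI"); and at month 12 ("will be asked to complete the Pittsburgh Sleep Quality Inventory (PSQI), and Insomnia Severity Index (ISI").
- **Size and entry**: Research Design and Methods expects at most 20 subjects in the one-year phase and says that not all are likely to join. The Sustained Efficacy Phase section makes joining voluntary, with a second consent.

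The documents give no missing-data method, analysis set, dropout assumption, significance level or PSQI standard deviation for this phase. They do not say whether the T-test is paired.

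**The concern.** The aim is sustained efficacy over a year, in a voluntary phase with no control arm. Two features of the analysis fit that aim poorly.

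First, a before-after test on month-12 values says nothing about subjects who left earlier, although their PSQI at months 3, 6 or 9 would show how they were doing. If those who were not improving are the ones who leave, the remaining subjects look better than the group that started, and there is no comparator to reveal it.

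Second, the ANOVA compares months 3, 6, 9 and 12 with one another. Its null hypothesis is that these four means are equal. A large fall by month 3 that then holds steady satisfies that null, and so does no change from baseline at all. The test as listed cannot tell these apart, yet the endpoint is the change from before treatment.

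**Working it through.** The plan states no figure to reproduce. The facts come from setting its sections side by side; the sizes are illustrations on assumed inputs.

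**1. Collected against analysed (one-year phase)**

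| Measure | Scheduled | Used in the stated analysis |
|---|---|---|
| PSQI | baseline, months 3, 6, 9, 12 | baseline, month 12 |
| ISI | baseline, months 3, 6, 9, 12 | months 3, 6, 9, 12 |
| TST, WASO (actiwatch) | baseline, then before each follow-up | months 3, 6, 9, 12 |

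PSQI loses three visits and the ANOVA loses baseline. The two-week PSQI at Visit 4 is also outside the one-year test.

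**2. Who is left in each test.** A paired T-test needs both values, so it keeps only those with a month-12 PSQI. A classical repeated measures ANOVA needs every visit. With an assumed 10% missing independently at each of four visits, 0.9^4 = 0.656, so about 66% remain: 0.656 × 20 = 13 subjects.

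**3. Precision of the month-12 change.** Compared: a mixed model on all visits, with separate visit means and the covariance treated as known, and the completers-only paired test. Assumed correlation is 0.5 to 0.85, compound symmetry or AR(1).

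| Reaching month 12 | Standard error ratio, model to paired test | Effective n |
|---|---|---|
| 20 of 20 | 1.00 | 20 |
| 16 of 20 | 0.94 to 0.97 | 17.0 to 18.1 |
| 12 of 20 | 0.88 to 0.94 | 13.6 to 15.6 |

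So there is no gain with complete data and a standard error 3 to 12% smaller with 12 to 16 completers.

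**4. Bias under dropout, large sample.** Assumed PSQI means are 12 at baseline, then 10, 10.5, 11 and 11.5, with SD 3. The true change is 11.5 − 12 = −0.5. Dropout after months 3, 6 and 9 has log-odds −2.2 + 0.5x, and 59 to 68% complete.

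| What drives dropout | x | Completers' change | Likelihood estimate, all visits |
|---|---|---|---|
| Last PSQI level | last − 10.5 | −0.49 to −0.56 | −0.49 to −0.51 |
| Lack of improvement | last − baseline + 1.5 | −0.72 to −1.86 | −0.50 to −0.51 |

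Under the second mechanism the completers' bias runs from −0.72 + 0.5 = −0.22 to −1.86 + 0.5 = −1.36 points. Dropout here depends only on observed PSQI, which is the condition under which the likelihood estimate is expected to work.

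**5. False positives with no true change.** Assumed 20 starters, SD 3.5, about half completing, correlation 0.5 to 0.85.

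- Dropout on last PSQI level: completers' mean change within 0.04 points of zero, rejection about 5%.
- Dropout on lack of improvement from baseline: a false fall of about 0.4 to 1.9 points, rejection 9 to 23%.

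The second result moves with the assumed strength of dropout. Other settings of the same mechanism gave 0.26 to 2.4 points and 7 to 36%.

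**The case against.** The T-test aims at the stated endpoint, one year against pre-treatment, and step 3 shows that with complete data the interim visits add nothing to that contrast. This stands: a reader might infer that ignoring three visits wastes power in itself, and it does not.

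A reader might also infer that the completers' comparison will show improvement where there is none. The documents do not support that. They give no attrition figure for the one-year phase and no reason for leaving, and the bias vanishes if dropout follows the last PSQI level alone. The most that can be said is that the comparison may mislead.

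That the test is completers-only is itself an inference from a within-subject design and a silent missing-data plan. An unpaired test would keep every baseline value, but it would ignore the pairing and still have no month-12 value for leavers. Likewise, the ANOVA wording may be shorthand that takes baseline for granted; but the same sentence names baseline for PSQI and not for the ANOVA.

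On sphericity, a reader might infer an inflated ANOVA. The plan does not say whether a correction will be applied. Without one, simulated type I error under AR(1) correlation was about 6 to 7.5%, which is minor.

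Finally, a mixed model is no cure-all at this size. Five visits with an unstructured covariance need 5 × 6 / 2 = 15 parameters from at most 20 subjects. In simulations without a small-sample correction (about 11 of 20 completing), that model rejected in 9 to 14% under the null, against 5 to 9% for the completers' T-test in the same runs. This stands and shapes the fix.

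**Conclusion.** The point holds in a limited form. It is certain from the text that PSQI at months 3, 6 and 9 has no planned use, that the Arm 1 section and the quarterly visit section disagree on when PSQI is measured, that the ANOVA as listed omits the baseline its endpoint needs, and that no missing-data rule exists.

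The size is conditional. It is nil with complete data and near nil if dropout depends only on the last PSQI level. It is a false fall of about 0.4 to 1.9 points with 9 to 23% rejection if subjects who have not improved from baseline leave and about half complete. The SD, correlation, dropout rate and dropout mechanism are all assumptions. The interim PSQI values would help to show which mechanism applies.

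The change should be made before analysis. It does not address selection at entry to the phase, because those who join are volunteers from the short study.

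**What to change.** In Specific Aims, Arm 1, replace the T-test and the ANOVA with one mixed model for repeated measures per outcome (PSQI, ISI, TST, WASO):

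- Include baseline and months 3, 6, 9 and 12, with all available visits from every subject in the phase. Take baseline TST and WASO from the actiwatch, as at follow-up.
- Fit by REML with a parsimonious covariance structure and Kenward-Roger degrees of freedom. Use an unstructured covariance only if it converges, with the same correction.
- Report the month-12-minus-baseline contrast, with its confidence interval, as the primary result.
- Add a sensitivity analysis for data not missing at random.
- Reconcile the Arm 1 statement of PSQI at year 1 with the collection at months 3, 6 and 9.

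The cost is analysis wording and slightly more analysis work; the data are already scheduled. The main result will then rely on a missing-at-random assumption, which is why the sensitivity analysis is needed. No wider interval is expected in principle: on the assumptions in step 3 the standard error is equal or 3 to 12% smaller, although that calculation treats the covariance as known and the gain in practice will be less.

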### **Arms 2**

**Aim 2:** To test the hypothesis that patient with Insomnia and comorbid Migraine will have longer, more consolidated sleep with lesser migraine frequency/intensity after treatment with BioBoosti.

## **BACKGROUND AND SIGNIFICANCE**

Provide a brief paragraph summarizing prior experience important for understanding the proposed study and procedures.

Insomnia is a leading health complaint, seen in almost 25% of the population. Insomnia complaints can be associated not only with discomfort for the patient, but also with loss of productivity, poor health, and a higher healthcare utilization. Insufficient or poor quality sleep increases the risk of a variety of disorders, leading to abnormalities of endocrine (Buxton, Pavlova et al 2010) and immune function (Lange et al 2011). Insomnia probably has the some of the same consequences as insufficient sleep from other causes. For example, in a recent study in our group (Buxton, Pavlova et al, 2011), we found that sleep fragmentation, as measured by wake after sleep onset (WASO), predicts diabetes risk in insomnia patients.

Treatment of insomnia is particularly challenging among patients with comorbidities, where insomnia is also more common. For example, insomnia is seen in 40-51% of patients with epilepsy (Vendrame 2013, Lopez et al 2013). Many studies indicate that patients with epilepsy frequently have fragmented sleep, as well as excessive daytime somnolence (Holoway et al 2011, Meyer et al 2011, Manni et al 2010, Krishnan et al 2012). Yet treatment of insomnia in these patients is very challenging, as many of the

frequently used medications may interact with antiepileptic medications, or affect seizure threshold. For example, benzodiazepines, which are among the most commonly used of treatment of insomnia, can be associated with withdrawal seizures, and are particularly risky in these patients. Similar considerations exist for the patients with cardiac disease and dementia. For example, although long term benzodiazepine use can be associated with frequent falls (Berry et al, 2015), impaired memory (Billioti et al, 2015) and even all-cause mortality (Iennum et al, 2015), they are frequently prescribed and needed. From a recent review (DeFrancesco, et al, 2015) it can be inferred that every fifth patient with Alzheimer’s disease will need benzodiazepine treatment.

Sleep disturbances can serve as a trigger for migraines, and insomnia in particular is a common comorbidity in patients with chronic migraine. Addressing insomnia in patients with chronic migraine can result in reductions in migraine frequency (Smitherman, et al, 2016)

The use of non-pharmacologic treatments of insomnia has gained much attention in recent years. For example, lectures on use of yoga in the treatment received a very high attendance at a recent CME course lead by the principal investigator of this study. This is only one example of the importance and high impact of any such research.

A safe, non-pharmacologic treatment of insomnia is very much needed to help patients with insomnia, especially those with comorbidities. Studies have tested the use of pulsed electromagnetic fields on bone healing (Chalidis et al 2011), wound healing (Cheing et al 2014), peripheral nerve regeneration (Kim et al 2002), neuropathic pain in diabetics (Weintraub et al 2009), and cardiac function after a myocardial infarct (Hao et al 2014). A post-market follow up has shown that the Bioboosti, a device that emits micromagnetic fields, can be effective as an adjuvant therapy for a number of conditions including insomnia (Biomobie 2015). We propose a pilot study to assess the effectiveness of FDA approved Biomobie device (Bioboosti) for the treatment of insomnia.

